5.3.3 Interventions

A schematic representation of the protocol summary is shown in Figure 1.

5.3.3.1 Investigational Products

Oral ferrous sulfate is the natural health product used throughout this study, and will be provided to patients in 300mg (60mg of elemental iron) tablets.

Vitamin C is a natural health product used throughout this study, and will be provided to patients in 500mg tablets.

5.3.3.2 Acquisition and Formulation

Once randomization has occurred, a prescription for the dosing regimen will be given to the patient to bring to pharmacy at the local site. Patients opting for virtual clinic visits will have their prescription filled by the study coordinator, and the pills couriered to their address on file. Patients will also have the

option to pick-up their prescription from the study site (curbside pick-up). There will be two randomization groups, one for hemoglobin ≥ 100 g/L (Mild IDA) and one for hemoglobin < 100 g/L (Moderate IDA).

5.3.3.3 Packaging

The study drug will be shipped as bulk orders of tablets that will then be distributed into individual bottles by the pharmacy at the local site. The oral ferrous sulfate tablets will be packaged in bottles containing the corresponding amount of pills depending on which treatment arm the patient has been assigned to. One patient kit will contain a bottle of oral ferrous sulfate tablets and another standard package of Vitamin C pills that are to be taken along with the study drug.

5.3.3.4 Treatment Assignment Procedures

Once enrolled, patients will be randomized to either the daily, or every other day treatment arm through the randomization procedure described in section 5.3.2.

5.3.3.5 Daily Dosing

Starting on Day 1, patients will take ferrous sulfate 300mg (60 mg elemental iron) on an empty stomach with vitamin C 500mg daily for a period of 12 weeks. Patients will be instructed to take oral iron at bedtime but can take it at another time during the day if more convenient. If patients cannot tolerate the oral iron on an empty stomach, they will be instructed to take it with a small amount of food, as long as dairy and tannins are not ingested at the same time.

5.3.3.6 Every other day dosing

Starting on Day 1, patients will take ferrous sulfate 300mg (60 mg elemental iron) on an empty stomach with vitamin C 500mg every other day for a period of 12 weeks. Patients will be instructed to take oral iron at bedtime but can take it at another time during the day if more convenient. If patients cannot tolerate the oral iron on an empty stomach, they will be instructed to take it with a small amount of food, as long as dairy and tannins are not ingested at the same time.

5.3.4 Adherence and Dose Modification

This is a pragmatic trial. Adherence will be documented by patients by providing a patient diary (see Supporting Documents) which shows the days on which they are supposed to take oral iron. This will be provided in a paper format. The research team will remind the patient to fill in their patient diary at 4 and 8 weeks. At the 12 week visit, the patient will be instructed to bring in their patient diary and pill bottle. A pill count will also be done to confirm adherence.

It is anticipated that ~ 30% of patients may not tolerate oral iron. The patient adherence diary instructions (see Supporting Documents) can be referred to for simple instructions (under point # 5) if the patient is having mild symptoms with the oral iron. Side effects may improve over the initial 1-2 weeks of oral iron. However, in some cases, patients may not be able to tolerate oral iron. Patients will be instructed to follow their planned schedule as prescribed. If they continue to have symptoms, patients will be instructed to step down in frequency (e.g. from daily to every other day; from every other day to two times per week; from two times per week to once per week) and to record how frequently they are able to take oral iron.

If patients are unable to take the oral iron at all, they will be continued to be followed as long as they are willing to continue and do not meet any criteria for withdrawal. Please refer to Section 10. Criteria for withdrawal from study.

5.3.5 Receiving, Storage, Dispensing and Return

5.3.5.1 Receipt of Investigational Product

McKesson Canada Corporation will act as the distributor for the oral ferrous sulfate supplements, and ship the tablets to Pharmacy at the local sites. The tablets will be transported under temperature controlled conditions. Once received, an inventory will be performed on the study product by study staff to ensure the correct product and amount were delivered, and the integrity of the product was not compromised during transportation. As such, any damaged or unusable product will be documented on the receipt log and the principal investigator will be notified.

5.3.5.2 Storage and Stability

Upon receipt of the product, the ferrous sulfate tablets require special handling and will be transferred to a temperature controlled area of the pharmacy, which is regularly monitored for quality assurance.

5.3.5.3 Dispensing of Investigational Product

The iron tablets will be provided in a bottle, with a child safety cap, to patients by the Pharmacy. The participants will be told how often they are to ingest the tablets, based on which treatment arm they have been randomized to, and will also be given a patient diary specific to their regimen that will be used for patient adherence. The patients will be directed to keep the study supplements at room-temperature conditions.

5.3.5.4 Return and Destruction of Investigational Product

Participants will be made aware of their responsibility to return any unused ferrous sulfate tablets at the end of the 12 week treatment duration, they will bring in the unused tablets and original study bottle back to the research team during their 12 week in-person visit to the local study site. A remote/telephone visit for the week 12 follow-up is also acceptable given the current situation with COVID-19. Virtual visits will also be an option post-COVID-19. Patients opting for a virtual 12-week clinical visit will be requested to courier their pill bottles and adherence diary back to the local site. In this case, a pre-paid return envelope will be provided. Patients will also have the option to return their pill bottles and adherence diary via curbside drop off.

5.4 Study Visits and Assessments

5.4.1 Baseline Visit and Assessment

Baseline assessment will occur according to the schedule below and may be performed in person/remotely (telephone/zoom/OTN). The following assessments will be completed at baseline:

5.4.1.1 Screening and enrollment will occur within 1 week of randomization

Case logs will be initiated for each referral meeting inclusion criteria, indicating:

- Any applicable exclusion criteria as listed in 5.2.2
- Reason for lack of consent amongst eligible patients
- Protocol violations for enrolled patients

Medical history:

- Demographics: age, sex, height, weight
- Diagnosis (reason for iron deficiency anemia, if known)
 - Example: gynecological, gastrointestinal, urologic, blood donation

- History of observed bleeding in the past 2 months: Y/N
 - Location of bleeding
 - Severity by WHO grade 1-3 (see Appendix A)
 - If menstrual bleeding, use validated tool (see Appendix B)
- Diet
 - Vegetarian
 - Vegan
- Blood Donation: Y/N
 - Number of times in past year?
 - Number of times in past 4 months?
- Comorbidities
 - Rheumatologic disorders: e.g. SLE, rheumatoid arthritis
 - Smoking
- Medication history at time of enrollment
 - Ranitidine
 - Proton pump inhibitor use
 - Medications
 - Other vitamin supplements (not including iron)
- History of oral iron use: Y/N
 - Any iron use in the past year: Y/N
 - If yes, last oral iron intake: (date)
 - Type of oral iron and tolerability
- History of IV iron use in the past year: Y/N
 - Type of IV iron

Questionnaire:

- FACIT-Fatigue scale (see Supporting Documents)

5.4.1.2 Baseline Laboratory Assessment

- Hemoglobin, reticulocyte count, ferritin, serum iron, TSAT, C reactive protein within 2 weeks of randomization (and at least 2 weeks off any oral iron supplementation)
- Creatinine within 3 months of randomization
- Screening bloodwork can be used for the baseline laboratory assessment

5.4.2 Follow-up Visits and Assessments

5.4.2.1 Week 1

Participants will be contacted by telephone or email for the following assessment at Day 7 ± 3 days

- Adherence as determined by patient diary (supporting documents)
- Side effect questionnaire (supporting documents)

5.4.2.2 Week 4

Participants will be contacted by telephone or email at Day 28 ± 7 days for the following assessment

- Adherence as determined by patient diary
- Side effect questionnaire
- FACIT-fatigue scale questionnaire
- Medication history (to confirm if any new or discontinued medications)
- Reminder to do laboratory tests (at the local site or local lab) for CBC, reticulocyte count

At the week 4 assessment, if the participant has a drop in hemoglobin of more than 10 g/L from baseline, then the patient will be referred back to the most responsible physician for management and escalation of therapy. If the patient receives escalation of therapy (need for alternative oral iron therapy including if a participant in the every other day group escalates to daily iron, need for intravenous iron, need for transfusion, visit to emergency department related to anemia), the participant will no longer complete any further study assessments and the most responsible physician will be notified. The reason for the drop in hemoglobin will be classified as: ongoing bleeding; non-compliance (defined as less than 50% of pills); other reason; or no clear reason.

5.4.2.3 Week 8

Participants will be contacted by telephone or email at Day 56 ± 7 days for the following assessment

- Adherence as determined by patient diary
- Side effect questionnaire
- FACIT-fatigue scale questionnaire
- Medication history (to confirm if any new or discontinued medications)

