8.2 Final Analysis Plan

The results of this pilot trial will be used to assess the feasibility and inform the design of the definitive trial. We will present point estimates of feasibility events, including enrolment, adherence to protocol and accrual, as proportions with 95% confidence intervals. We will present continuous data as means and standard deviations, or medians and inter-quartile ranges, as appropriate.

An intention-to-treat analysis will be performed on all patients randomized for the secondary efficacy outcome. A per protocol analysis will be conducted for patients who have taken at least 90% of the

prescribed doses. Subgroup analysis will be performed on the stratified groups with hemoglobin 100g/L or greater and hemoglobin less than 100g/L. Additional subgroup analyses will include: patients with ongoing bleeding (WHO grade 2 or higher) vs no bleeding; and normal vs. increased CRP (based on the normal range).

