10.0 CRITERIA FOR WITHDRAWAL AND DISCONTINUATION FROM STUDY

Patients will be followed until 12 weeks or until there is an escalation of therapy as defined by need for: alternative oral iron therapy (including if a participant in the every other day group escalates to daily iron), need for intravenous iron, need for transfusion, or a visit to emergency department related to anemia.

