10.1 Early Termination and Reasons for Withdrawal

Patients may find that they are not able to continue in the study due to intolerable side effects from the oral iron despite simple measures to address the side effects. Patients are permitted to withdraw consent at any time if they desire and will not undergo further trial investigations if they do so.

Additionally, patients who become pregnant during the course of the study will be stopped from using the study medications and withdrawn from the study. Other reasons for withdrawal include use of

intravenous iron, use of blood transfusion, any deviation from inclusion/exclusion criteria and serious adverse events (as described in section 9.3).

Participants withdrawing from the study should be contacted by the study research team requesting a final visit and to follow up with any unresolved adverse events. Once withdrawn from the study, no further study procedures or evaluations should be performed, or additional study data collected. However, every effort should be made to obtain permission to document the reason for withdrawal and to collect participant outcomes, such as survival data up to the protocol-described end of participant follow up period, where possible. Any data collected prior to the withdrawal of consent may be retained and used by the sponsor. If the patient withdraws from the study, the research team will notify the patient's referring physician.

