10.2 Data Collection and Follow-up for Withdrawn Participants

Patients will be asked to continue with follow-up quality of life assessment and laboratory tests. It is important to continue to follow these patients and capture outcomes that occur once they have discontinued study intervention to determine feasibility. Through telephone calls and emails, every effort will be made to obtain permission to document the reason participants withdrew consent and to continue collecting the quality of life assessments and laboratory values previously mentioned. Patients who have completed at least 90% of the prescribed doses will be included in the per-protocol analysis.

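### Assessments stop at escalation of therapy in sections 5.4.2.2 and 10.0, while section 10.2 continues them; followed as written, the stopping rule removes week 12 values that the intention-to-treat analysis needs

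*Combined protocol and SAP*

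**What the plan says.** - **Stopping rule.** Section 5.4.2.2 refers a patient whose week 4 hemoglobin is more than 10 g/L below baseline back to the treating physician. If therapy is then escalated, "the participant will no longer complete any further study assessments and the most responsible physician will be notified". Section 10.0 applies the same limit at any time: "Patients will be followed until 12 weeks or until there is an escalation of therapy". Both sections name four events: alternative oral iron (including a move from every other day to daily), intravenous iron, transfusion, and an anemia-related emergency visit.
- **Withdrawal.** Section 10.1 lists among the reasons "intravenous iron, use of blood transfusion, any deviation from inclusion/exclusion criteria and serious adverse events". It then says "Participants withdrawing from the study should be contacted by the study research team requesting a final visit" and "Once withdrawn from the study, no further study procedures or evaluations should be performed, or additional study data collected", followed by an exception: "every effort should be made to obtain permission to document the reason for withdrawal and to collect participant outcomes".
- **After withdrawal.** Section 10.2 says "Patients will be asked to continue with follow-up quality of life assessment and laboratory tests" and explains that outcomes after stopping the study intervention matter for judging feasibility.
- **Stopping or stepping down iron.** Section 5.3.4 keeps following patients who cannot take iron at all, while they are willing and meet no withdrawal criterion. Step-down does not end follow-up.
- **Schedule.** Appendix C has hemoglobin at baseline, week 4 and week 12; ferritin, serum iron and TSAT at baseline and week 12; FACIT-fatigue at baseline and weeks 4, 8 and 12.
- **Analysis.** Section 8.2: "An intention-to-treat analysis will be performed on all patients randomized for the secondary efficacy outcome". The Protocol Summary says the same for the secondary clinical outcomes. Neither gives a rule for missing or post-escalation values.
- **Escalation as an outcome.** Section 3.4 item 16 counts any alternative oral iron. The oral entry in section 5.4.2.4 and section 7.2 item 16 is only the move from every other day to daily.

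**The concern.** Section 7.2 defines the week 12 hemoglobin increment as the week 12 value minus baseline. A patient whose assessments ended earlier has no such value, so an intention-to-treat analysis of all randomized patients cannot be carried out from the planned data.

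The missing values would not be a random subset. One route to escalation is a fall in hemoglobin at week 4, so those who leave tend to be doing badly. The move from every other day to daily exists only in the experimental arm, so the loss may also differ by arm. The observed week 12 difference and SD, which section 8.1 wants for sizing the definitive trial, would then describe a selected group.

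The two escalation definitions add a scoring gap. A patient switched to another oral iron leaves assessments under 5.4.2.2 and 10.0, but is not an escalation under the wording of 5.4.2.4 and 7.2.

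**Working it through.** **1. The rules side by side**

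| Event before week 12 | 5.4.2.2 and 10.0 | 10.1 | 10.2 |
|---|---|---|---|
| Every other day to daily, or other oral iron | assessments end | not listed as withdrawal | continues labs and quality of life, if read as covering anyone who stopped study treatment |
| Anemia-related emergency visit | assessments end | not listed | same |
| Intravenous iron, transfusion | assessments end | withdrawal; no further data by default, exception by permission | continues labs and quality of life |
| Step-down or stopping iron (5.3.4) | not affected | not affected by itself | not needed; follow-up continues |

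Sections 10.1 and 10.2 can be reconciled as meaning that data continue with permission, but their defaults are opposite. Neither says whether it overrides 5.4.2.2 and 10.0.

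**2. The plan's own numbers**

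Table 2, true difference 0, SD 5, margin 5, 90% power, one-sided 5%: n per arm = 2 × (1.645 + 1.282)² × 5²/5² = 17.1, so 18 per arm and 36 in total. Then 36/0.70 = 51.4, rounded to 52. Both stated figures reproduce. The plan does not say whether escalation is part of the 30% drop-out.

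**3. Size for the week 4 route**

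The documents give no escalation rate. Assumptions:

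- the week 4 increment is normal with mean m = 5 or 10 g/L;
- its SD is s = 5, 7.5 or 10 g/L (the SDs of Table 2), and the same at week 12;
- the correlation of week 4 and week 12 increments is ρ = 0.5 to 0.75;
- every patient below −10 g/L escalates and is lost.

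Formulas:

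- P = Φ((−10 − m)/s)
- chance of at least one trigger in 52 = 1 − (1 − P)^52
- d = ρ × (mean week 4 increment of those retained − mean of those triggered), the expected week 12 gap between the two groups
- bias if only one arm loses patients = P × d
- SE of the difference with 18 per arm = s × √(2/18), that is 1.67, 2.50 and 3.33 g/L for s = 5, 7.5 and 10

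| m | s | P | At least one in 52 | d, g/L | One-arm bias, g/L | Bias/SE |
|---|---|---|---|---|---|---|
| 10 | 5 | 0.003% | 0.16% | 10.6–15.8 | 0.0003–0.0005 | <0.001 |
| 5 | 5 | 0.13% | 6.8% | 8.2–12.3 | 0.011–0.017 | 0.01 |
| 10 | 7.5 | 0.38% | 18% | 11.2–16.8 | 0.04–0.06 | 0.02–0.03 |
| 5 | 7.5 | 2.28% | 70% | 9.1–13.7 | 0.21–0.31 | 0.08–0.12 |
| 10 | 10 | 2.28% | 70% | 12.1–18.2 | 0.28–0.41 | 0.08–0.12 |
| 5 | 10 | 6.68% | 97% | 10.4–15.6 | 0.69–1.04 | 0.21–0.31 |

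With equal loss in both arms the expected bias is 0. The other routes to escalation are not quantified.

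**4. Completion proportions**

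Each patient whose assessments the protocol stops before week 12 counts as a non-completer in section 7.2 items 3 to 5. With 52 patients that is 1/52 = 1.9 percentage points per patient.

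**The case against.** **Section 10.2 may already cover everyone.** Section 10.0 sits under the heading on withdrawal and discontinuation and lists all four events. Section 10.2 belongs to the same chapter and speaks of patients who have discontinued study intervention. On that reading every escalated patient is asked for blood tests and FACIT-fatigue. This stands as a possible reading, but it contradicts 5.4.2.2 and 10.0 directly, so the sections still need reconciling. A reader might infer from the shorter list in 10.1 that oral escalations and emergency visits certainly lose week 12 data while only intravenous iron and transfusion are unclear. The documents do not support that split; the conflict concerns all four events.

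**The effect is small.** This stands. The worst case in the table is 0.31 SE and requires loss in one arm only. With the SD of 5 that underlies the 36/52 row, a week 4 trigger is unlikely in the whole trial. Referral need not lead to escalation either.

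**The arm imbalance is limited.** This stands in part. Alternative oral iron is open to both arms; only the move from every other day to daily belongs to one arm.

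**Feasibility is judged for the design as it is.** Section 7.1 says so, and Appendix C checks escalation at weeks 1, 4, 8 and 12, so escalated patients can be identified. That allows them to be shown separately, but does not supply the missing week 12 values.

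**The definition mismatch is a wording matter.** Medication history at weeks 4, 8 and 12 could reveal another oral iron. It would still be unclear whether to score it.

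**Conclusion.** The concern holds as a conflict between sections that needs no assumed rate: 5.4.2.2 and 10.0 end assessments at escalation, 10.2 continues them, 10.1 lies between, and no precedence is given. Followed as written, the first two remove week 12 values that the planned analysis needs, in a way related to outcome and possibly different by arm. It should be fixed, because values not collected cannot be recovered.

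The expected size is small. For the week 4 route under the assumptions above, the chance of at least one trigger in 52 is about 0.2% to 97%, and the one-arm bias is under 0.001 to 1.0 g/L, at most about 0.3 SE. The primary outcome, time to enroll 52 patients, is unaffected.

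Two stronger readings are not supported:

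- A reader might infer that any change of oral iron regimen ends follow-up. Section 5.3.4 shows that step-down and stopping do not.
- A reader might infer a bias toward non-inferiority that is large against the 5 g/L margin. For example, assumed escalation of 15% against 5% and an assumed deficit of 20 g/L would give (0.15 − 0.05) × 20 = 2 g/L. Neither rates nor deficits are in the documents, and the direction depends on which arm loses more patients and how they would have done.

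**What to change.** - Reconcile sections 5.4.2.2, 10.0, 10.1 and 10.2 into one rule: escalation alone does not end the scheduled contacts or the week 12 blood tests for patients who still consent to data collection. Withdrawals for other reasons, such as pregnancy or a serious adverse event, are outside this change.
- Record the date and type of each escalation.
- Use the week 12 values of escalated patients in the intention-to-treat analysis. Add a sensitivity analysis that scores escalation as non-response for complete hemoglobin response, because values after rescue can pull the arms together and so favour non-inferiority.
- Use the definition in section 3.4 item 16 in sections 5.4.2.4 and 7.2. Report moves from every other day to daily separately, since only one arm can have them.
- Show escalated patients separately in the completion proportions.

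The cost is protocol wording, plus calls and one blood draw that are already scheduled, for few patients. The change concerns data collection and scoring only; clinical management is unchanged. It does not recover what would have happened without rescue, and it does not replace a missing-data method for ordinary drop-out.

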5.4.2.4 Week 12 Final Study Visit

Participants will be assessed in person/remotely (telephone/zoom/OTN) at Day 84 ± 7 days for the following assessment

- Adherence as determined by patient diary and pill count
- Side effect questionnaire
- FACIT-fatigue scale questionnaire
- Medication history (to confirm if any new or discontinued medications)
- Laboratory tests: CBC, reticulocyte count, ferritin, serum iron and TSAT
- Need for escalation in therapy: Y/N
 - Increase in oral iron regimen from every other day to daily
 - Intravenous iron
 - Transfusion
 - Visit to emergency department related to anemia

5.4.2.5 Week 13

Participants will be contacted by telephone or email at $7 \text{ days} \pm 3$ days after the Week 12 final study visit for assessment of adverse and serious adverse events.

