- A. Increment will be calculated from each subject first, and then mean increment for each study group. A difference in the mean increment will be calculated as mean increment in the every other day oral iron group minus mean increment in the daily oral iron group.
- B. Standard deviation (SD) was not available for the increment. It could be estimated from SDs of the pre- and post- treatment hemoglobin level and assumed correlation between pre- and post-hemoglobin. If SDs for the pre- and post- hemoglobin are equal to 10, and correlation between them is 0.5, the estimated SD for the increment is 10. If the correlation between pre- and post- is 0.75, then the estimated SD for the increment is 7.1.
- C. One sided 95% confidence interval of the difference between two groups in the hemoglobin increment will be calculated (every other day minus daily). If the bound of the confidence interval is greater than -5, then non-inferiority can be confirmed.
- D. If we assume the true difference between two groups is -0.15 as reported from the meta-analysis, the sample size required could be slightly larger.
- E. Total sample size was divided by 70% to account for a 30% drop out.

Given that this pilot trial is a proof-of concept study, a sample size of 52 patients was deemed appropriate. Therefore, we will aim to enroll 52 patients to determine the feasibility of the trial and to provide more accurate estimates of the numbers required for a definitive trial. The trial will be deemed feasible if we are able to enroll 52 patients over 2 years at two sites.

The trial will proceed until there are 52 enrolled patients and at least 36 patients who complete the trial to 13 weeks.

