9.0 ASSESSMENT OF SAFETY

9.1 Definitions

9.1.1 Adverse Event

An **Adverse Event (AE)** is defined as any new event that may jeopardize the patient which the study investigator physician perceives may be directly related to the enrolment in the pilot study or to the assigned arm. Adverse events are not study related if they are related primarily to the underlying disease. All AEs are to be documented and assessed for relatedness. If related to the study drug and occurring from baseline up to one week after the final study visit, the AE will be recorded on the eCRF and coded as per the most recent edition of the Common Terminology Criteria for Adverse Events (CTCAE).

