APPENDIX C:

Table 1: Flow Chart of Assessments/Procedures to be Performed Throughout the Study

Procedures	Prior to Enrolment	After Enrolment	Week 1 (±3 days)	Week 4 (±7 days)	Week 8 (±7 days)	Week 12 (±7 days)	Week 13 (7 days ± 3 days after final study visit)
Referring clinician offices identify potential patients as participants	X						
Patient (surrogate) informed consent	X						
Inclusion and exclusion criteria	X						
Randomization		X					
Baseline Data							
Case Logs (reason for lack of consent, protocol violations)	X						
Medical History		X					
Laboratory Assessments							
Hemoglobin	X			X		X	
Reticulocyte Count	X			X		X	
C reactive protein (CRP) – acute phase reactant	X						
Ferritin	X					X	
Serum Iron	X					X	
Transferrin Saturation (TSAT)	X					X	
Creatinine clearance	X						
Subjective Patient Assessments							
FACIT-Fatigue Scale Questionnaire		X		X	X	X	
Patient Diary Adherence			X reminder	X	X	X	
Side Effect Questionnaire				X	X	X	
Pill Count						X	
Adverse and Serious Adverse Events			X	X	X	X	X
Need for Therapy Escalation			X	X	X	X	

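### The Week 13 safety contact may be made before the one-week post-visit adverse event window closes, and no later contact is scheduled

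*Combined protocol and SAP*

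**What the plan says.** **Adverse event window.** Section 9.1.1 has a drug-related event entered on the eCRF if it is "occurring from baseline up to one week after the final study visit". The end of the window is tied to the visit.

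**Final visit.** Section 5.4.2.4 places it "at Day 84 ± 7 days for the following assessment", in person or remotely.

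**Contact after the visit.** Section 5.4.2.5 schedules one telephone or email contact, at 7 ± 3 "days after the Week 12 final study visit for assessment of adverse and serious adverse events". The Appendix C column reads "Week 13 (7 days ± 3 days after final study visit". Nothing is scheduled after it.

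**How events are found.** Section 9.2.5 has the team look for adverse events at each participant contact, by questioning and, where appropriate, examination.

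**Dosing period.** Both arms start on Day 1. Section 5.3.3.5 gives iron "with vitamin C 500mg daily for a period of 12 weeks" and section 5.3.3.6 gives it "with vitamin C 500mg every other day for a period of 12 weeks".

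**End of treatment.** The Protocol Summary equates the interval from first dose to final visit with 12 weeks. Section 5.3.5.4 has unused tablets returned when the 12 weeks of treatment end, at the visit, and adds: "A remote/telephone visit for the week 12 follow-up is also acceptable". In that case bottle and diary come back by courier or drop-off. Section 5.4.2.4 lists the pill count among the final-visit assessments, and section 5.4.4 places it after the 12-week supplementation period. None of these says whether dosing stops at a final visit held before Day 84.

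**The concern.** There are two separate issues.

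The first is a mismatch between two windows. Section 9.1.1 asks for a week of events after the visit, while section 5.4.2.5 lets the only later contact happen on the fourth day of that week. Under section 9.2.5 the contacts are how events are actively sought, so a contact made early but within its allowed window ends active ascertainment before the recording window closes. The Week 13 contact has no other stated purpose.

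The second is the anchor. The contact and the recording window both count from the visit and neither refers to the last dose. The visit can be held a week before the 12 weeks of dosing are over, and a remote visit does not in itself remove the tablets from the patient. If dosing then continues to schedule, the last safety contact could precede the last dose.

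What is at stake is the completeness, and the comparability between patients, of the late adverse event data. The Week 13 contact feeds none of the outcomes listed in section 7.2, where side effects are assessed at weeks 4, 8 and 12. The primary outcome, time to enrol 52 patients, is not affected.

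**Working it through.** **Inputs**

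- Visit day v: Day 84 ± 7, so 77 to 91, which is 15 possible days (section 5.4.2.4).
- Contact offset k: 7 ± 3 days after the visit, so 4 to 10, which is 7 possible days (section 5.4.2.5, Appendix C).
- End of the adverse event window: v + 7 (section 9.1.1).
- Last scheduled dose L, counting the first dose as Day 1 on the same scale as the visit days. Daily: 12 × 7 = 84 doses, the last on Day 84. Every other day: Days 1, 3, …, 83, which is 42 doses, the last on Day 83 (sections 5.3.3.5 and 5.3.3.6).

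**The plan's own figure.** Nominal contact day = 84 + 7 = Day 91, and 91 / 7 = 13.0 weeks. The Week 13 label reproduces.

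**Part 1: window days without scheduled questioning**

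Uncovered days = max(0, (v + 7) − (v + k)) = max(0, 7 − k). The visit day v cancels.

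| Contact on day | +4 | +5 | +6 | +7 to +10 |
|---|---|---|---|---|
| Uncovered days of 7 | 3 | 2 | 1 | 0 |

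The largest gap is 3 of 7 days (43%). It is the same for a visit on Day 77, 84 or 91, because window and contact share one anchor. It comes only from the 3-day tolerance before the nominal date.

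**Part 2: contact relative to the last scheduled dose**

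Contact day = v + k. Earliest: 77 + 4 = Day 81. Latest: 91 + 10 = Day 101. Against Day 84, that is from 3 days before to 17 days after the last scheduled daily dose.

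Allowed visit/contact pairs: 15 × 7 = 105. Pairs with v + k < L:

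- Daily (L = 84): (77, +4), (77, +5), (77, +6), (78, +4), (78, +5), (79, +4), so 6 of 105.
- Every other day (L = 83): (77, +4), (77, +5), (78, +4), so 3 of 105.

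These are counts of permitted combinations. They are not probabilities, since the documents do not say how visits and contacts will spread over their windows.

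In the extreme case, a contact on Day 81, the daily arm still has scheduled doses on Days 82, 83 and 84, and the every-other-day arm has one on Day 83. With a Day 77 visit the recording window closes on 77 + 7 = Day 84, the day of the last scheduled daily dose.

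**Effect of a lower limit of +7**

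Uncovered days = max(0, 7 − 7) = 0 for every visit day. The earliest contact becomes 77 + 7 = Day 84, which no longer precedes the last scheduled dose in either arm. It would still give only 84 − 84 = 0 days (daily) or 84 − 83 = 1 day (every other day) after that dose. The lower limit alone therefore settles Part 1 but not the anchor question in Part 2.

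**The case against.** The strongest reply is that the protocol treats the final visit as the end of treatment. The Protocol Summary makes first dose to final visit 12 weeks, section 5.4.2.4 does the pill count at that visit, and section 5.3.5.4 brings the tablets back then. On that reading no dose follows the visit and Part 2 disappears. This is a fair reading but not the only one. Sections 5.3.3.5 and 5.3.3.6 fix the dosing period at 12 weeks without reference to the visit, section 5.4.4 puts the pill count after that period, and a remote visit separates the visit from the tablet return. Part 2 stands only as a point to reconcile.

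A second reply is that section 9.1.1 defines recordable events by when they occur, not by when the contact is made. An event volunteered on day 6 after a day 4 contact can be recorded, and section 9.3.5 runs serious event reporting from site awareness. This stands: the gap is in scheduled questioning only.

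A reader might also infer stronger conclusions that the documents do not support:

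- *That the 3-day gap results from an early, Day 77 visit.* It does not; the visit day cancels.
- *That a promised post-treatment week is not delivered.* Section 9.1.1 promises a week after the visit, not after the last dose.
- *That early remote visits leave no off-treatment safety observation.* Even with a Day 77 visit, a contact at +8 to +10 (Days 85 to 87) falls after the last scheduled dose in both arms.
- *That the section 9.1.2 statement on side effects resolving when iron is stopped is left untested.* That is background on expected risk, and no listed outcome tests it.
- *That the requirement in section 8.1 for "at least 36 patients who complete the trial to 13 weeks" would be met by patients last contacted in week 12.* Section 8.1 does not define completion for this purpose, so no effect on the count is shown.

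**Conclusion.** The mismatch between section 9.1.1 and the Week 13 window is real and rests on the text alone: up to 3 of the 7 post-visit days can lack scheduled adverse event questioning, for any visit day. The only assumption is that a contact covers events up to the day it is made.

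The dose-overlap issue is narrower and conditional. It needs a final visit on Days 77 to 79 (daily) or Days 77 to 78 (every other day), a contact before day +7, and dosing that continues after the visit. The documents do not settle the last of these.

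Both issues concern secondary safety data. This is a worthwhile tidy-up, not a threat to the trial's conclusions.

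**What to change.** 1. In section 5.4.2.5 and Appendix C, change the Week 13 window to 7 to 10 days after the final study visit, so that the contact always covers the whole section 9.1.1 window.
2. Reconcile the Protocol Summary and sections 5.3.3.5, 5.3.3.6, 5.3.5.4, 5.4.2.4 and 5.4.4 on whether dosing continues after a final visit held before Day 84. Which rule applies is for the investigators to decide.
3. If dosing can continue, record the date of the last dose on the CRF, and time both the Week 13 contact and the section 9.1.1 window from the later of the final visit and the last dose.

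**Cost.** The contact window shrinks from 7 days (+4 to +10) to 4 days (+7 to +10), so a few more contacts may fall outside it. No contact is added. The first change touches two places in the protocol. The third, if needed, also touches section 9.1.1 and adds one CRF date field.
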